## LIST OF ABBREVIATIONS

AE	Adverse Event
cm	centimeter
eCRF	Electronic Case Report Form
EISO	East Indian Sandalwood Oil
FAS	Full Analysis Set
g	gram
ITT	Intent-to-Treat
kg	kilogram
MedDRA	Medical Dictionary for Regulatory Activities
N	population size (N for sample size, n for available data)
PASI	Psoriasis Area and Severity Index
PGA	Physician's Global Assessment
PP	Per Protocol
PT	Preferred Term
SD	Standard Deviation
SOC	System Organ Class
TEAE	Treatment Emergent Adverse Event

---

Note: The first occurrence of some abbreviations is not spelled out in the document (e.g. units of measure).

## 1.0 STUDY INTRODUCTION

This statistical analysis plan is based on the protocol “A Double Blind, Multi-Center, Randomized, Placebo Controlled Safety, Tolerability, and Efficacy Trial of a New Botanical Drug Product Containing East Indian Sandalwood Oil (EISO) at One Dose Level for the Treatment of Mild-to-Moderate Plaque Psoriasis in Adult Subjects”, dated 08 August 2017.

### 1.1 Study Objectives

#### 1.1.1 Primary Objectives

The primary objective of this study is to evaluate the safety of SAN021 compared to placebo when administered topically for up to 42 days to adults who have a clinical diagnosis of mild-to-moderate plaque psoriasis. Safety will be assessed by evaluating the number and percentage of subjects reporting at least one adverse event (AE) tabulated with respect to severity, duration, and relationship to the study drug.

#### 1.1.2 Additional Objectives

Additional objectives are to evaluate tolerability and preliminary efficacy. Tolerability will be assessed based on the number of subjects reporting discomfort during or immediately following application of study drug in the treatment areas. Discomfort will also be recorded as an AE. Preliminary efficacy will be assessed based on the following summaries:

- Percentage of subjects who have a  $\geq 25\%$  reduction in the Psoriasis Area and Severity Index (PASI) score at any point during the 42 days of treatment.
- Percentage of subjects who have a  $\geq 50\%$  reduction in the PASI score at any point during the 42 days of treatment.
- Percentage of subjects with a PGA score of “clear” or “almost clear” at any time during the 42 days of treatment.
- Percentage of subjects achieving at least a 1-grade improvement in Physician’s Global Assessment (PGA) score.
- Percentage of subjects achieving a 2-grade improvement in PGA score.

## 2.0 STUDY DESIGN

### 2.1 Overview of Study Design

This trial will be a double blind, multi-center, randomized, placebo controlled study to evaluate the safety, tolerability, and efficacy of SAN021 when administered topically for up to 42 days to adults between the ages of 18 to 65 years inclusive who have a clinical diagnosis of mild-to-moderate plaque psoriasis. Subjects will enter the Screening Period once the informed consent and photographic consent process has been completed. Subjects with mild-to-moderate plaque psoriasis, as defined by a PASI score between 2 and 12, that, in the opinion of the investigator, is appropriate for topical treatment, covers a minimum of 1.0% and a maximum of 10.0% body surface area in the permitted treatment areas, and who meet all of the inclusion and none of the exclusion criteria will be enrolled.

Once subject eligibility is confirmed and the screening procedures completed, all enrolled subjects will start the Treatment Period of the study. All enrolled subjects will receive either 10% SAN021

or placebo serum (randomized in a 2:1 ratio) with the first dose applied at the Day 1 Study Visit. Subjects will be instructed on how to apply the study medication twice daily for 42 days. Subjects will return to the clinic for study-related assessments on Study Days 7, 14, 28 and a final visit on Day 42. On Study Day 49, subjects will receive a follow-up phone call and be queried for condition status since going off study.

**Table 2.1: Visit Schedule**

Screening	Baseline[1]	← Treatment →				Follow-up Call[2]
Day -7 to 0	Day 1	Day 7 (±2 days)	Day 14 (±2 days)	Day 28 (±2 days)	Day 42 (±2 days)	Day 49 (±2 days)
	Visit 1	Visit 2	Visit 3	Visit 5	Visit 6	

[1] Screening and Baseline may occur on the same day provided the informed consent and photography consent process has been completed and the consents have been signed.

[2] Follow-up may be extended if adverse events require time to assess.

## 2.2 Sample Size

There is no formal assessment of sample size. The sample size of 72 subjects was chosen to ensure at least 60 subjects complete the study. The sample size is not expected to yield statistically significant results, and there are no inferential statistical analyses.

## 3.0 ANALYSIS POPULATIONS

### 3.1 Safety Analysis Set

The Safety Analysis Set is defined as all enrolled and randomized subjects who applied at least one treatment of the study drug.

### 3.2 Full Analysis Set

The Full Analysis Set (FAS) is defined as all randomized subjects who applied at least one administration of the study drug and who had at least one post-baseline efficacy assessment.

### 3.3 Per Protocol Analysis Set

The Per Protocol Analysis Set (PP) is defined as all randomized subjects who applied at least one administration of the study drug and who had at least one post-baseline efficacy assessment who do not have any major protocol violations, including:

- Violations of inclusion/exclusion criteria.
- Use of prohibited concomitant medications.
- Noncompliance (i.e., less than 60% compliant with study treatment), as determined by the average product usage for the duration of participation.
- Failure to provide a clinical observation at Day 42.
- A scheduled visit occurring more than 5 days outside of the +/- 2-day visit window.

Although non-compliance is defined in the protocol as <80% compliance with study treatment, subsequent consideration of subject medication use evaluated prior to study data unmasking lead to a reduction in the threshold to <60% compliance.

### 3.4 Other Analysis Sets

An Intent-to-Treat Analysis Set (ITT) is described in the protocol as all subjects enrolled who apply at least one treatment of the study drug or placebo. However, there is no analysis specific to the ITT population and it will not be used in the generation of any tables or listings.

The Enrolled Population is defined as all subjects who signed the informed consent. The Enrolled Population is equivalent to the ITT and is referred to in the generation of listings and tabulation of patient disposition.

## 4.0 STATISTICAL METHODS OF ANALYSIS

### 4.1 Statistical Considerations

Data listings and summary tables will be provided. Listings will include all data captured on the electronic case report form (eCRF) unless specified otherwise. Calculated (derived) variables will be listed as appropriate. Summary tables will be provided for select variables as described in Section 5 through Section 8. Analyses by visit will be performed on nominal visits regardless of actual visit day. The exception will be the case where a subject discontinued prior to Day 42 yet data were mistakenly logged in the Day 42 eCRFs, as Day 42 represents end of treatment. Here data will be analyzed on the appropriate study visit day according to the visit window in which the actual study day falls; this will allow for correct implementation of the last observation carried forward method.

#### 4.1.1 Quantitative Assessments

Quantitative assessments (continuous data) will be summarized by reporting the number of subjects (n), mean, standard deviation (SD), median, minimum value, and maximum.

#### 4.1.2 Qualitative Assessments

Qualitative assessments (categorical data) will be summarized by reporting the frequency (count and percent) of subjects falling within the category. Unless specified otherwise for a particular assessment, the denominator for calculating a percentage will be the total number of subjects in the analysis population for the subgroup being analyzed; for example, within study arm, the number of subjects within the study arm in the analysis population will be the denominator. For overall summaries, the total number of subjects in the analysis population will be used as the denominator.

### 4.2 Methods for Handling Missing Data

Missing efficacy data will be imputed using the last observation carried forward unless specified otherwise; unscheduled visit data will be included in the carry forward procedure. No imputations will be made for missing safety data.

## 5.0 EVALUATION OF SUBJECT DISPOSITION AND EXPOSURE

### 5.1 Subject Disposition

All analyses in this section will be performed using the Enrolled Population. Subject disposition in terms of all randomized, completed or discontinued status, and reason for discontinuation will be summarized for each study arm and over all study arms by count and percent. Analysis populations (FAS, PP, and Safety) will be summarized for each study arm and over all study arms by count and

percent. All percentages will be based on the Enrolled Population. Details of subject disposition and discontinuation status will be provided in a by-subject listing.

## 5.2 Study Product and Visit Compliance

All analyses in this section will be performed using the Safety Population. Study visit attendance will be summarized by study arm for each follow-up visit. The count and percent of subjects who attended their visit will be calculated.

Study product compliance parameters will be summarized using descriptive statistics for each study arm. These parameters include the following:

- Number of applications missed (quantitative assessment)
- Total weight of product used (quantitative assessment)
- Average weight per application of product (quantitative assessment)
- The number and percentage of subjects who received fewer than 60% of prescribed applications (and considered non-compliant with the treatment) at each visit, and over all follow-up visits.

Compliance will be based on the baseline body surface area (bsa) of the treated area times 0.25 ( $W=bsa \times 0.25$ ). The number of applications per study day is two, and will be assumed to be one on each visit day, except baseline, which will be assigned two applications. The number of applications (X) for an interval will then be:

- from baseline to a follow-up visit:  $X = (\text{current visit date} - \text{baseline date}) \times 2 + 1$
- from a follow-up visit to a subsequent follow-up visit:  
$$X = (\text{current visit date} - \text{previous visit date}) \times 2;$$

and therefore, the expected weight of drug applied (EW) will be calculated as:

$$EW=X(W)$$

The actual amount of drug applied in an interval (AW) will be the difference between the bottle weights at the relevant visits:

$$AW = \text{weight of bottle at current visit} - \text{weight of bottle at previous visit}$$

The actual compliance will be calculated as the percentage (C) of what was used versus what was expected to be used:

$$C = (AW/EW) \times 100$$

This value may be greater than 100%. However, if the value is less than 60%, then the subject will be considered non-compliant for that study treatment interval.

Using these same calculations, compliance over all follow-up visits will be calculated using available data from the medication dispensation log. Weight of drug used from a bottle will be the difference of the last medication weight reported and the weight of the bottle at dispensation. If multiple bottles are used, cumulative product weight will be calculated.

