## 9.0 CONVENTIONS FOR CALCULATIONS AND TABULATIONS

*Table 9.0 Conventions for Calculations and Tabulations*

CONVENTION	DESCRIPTION
Age calculation	Age is calculated as an integer in years as the difference between the subject's date of informed consent and the date of birth. Specifically, if a subject's birthday has been reached by the informed consent date then age will be the difference in years, otherwise age will be the difference in years minus 1.
Baseline	Baseline is defined as assessments completed on Visit 1 (Day 1) prior to the administration of the study drug unless otherwise specified.
Study Day	Date of visit or evaluation – baseline date + 1
Percentage calculation	Percentages are calculated as 100* numerator/denominator. Rounding is not necessary because rounding is handled by the display format. Denominator is the total number of subjects in a column group unless otherwise specified.
AE counting: treatment emergence	An AE will be considered treatment emergent if it begins on or after the time of the first study treatment application. If the start date is the same as the date of first application (Day 1), the times are not present, or there is no indication that the AE began before dosing, the event will be considered treatment emergent.
AE counting: general summary	In summary displays, AEs are counted only once per subject within a category (e.g., over all and preferred term).
AE counting: summary by assessment	When AEs are summarized within levels of another AE assessment (e.g., causality or severity), AEs are counted once per subject at the worst level of the assessment (e.g., least

CONVENTION	DESCRIPTION
	complementary relationship or greatest severity). A missing or unknown value for the assessment will be considered worst.
Change from Baseline	current visit value – baseline visit value
Percent Change from Baseline	((current visit value —baseline visit value) / baseline visit value) x 100

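### The by-visit non-compliance percentage keeps subjects without bottle weights in its denominator although they cannot enter its numerator, so it is diluted as weights go missing

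*SAP*

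**What the plan says.** SAP 5.2 opens with the population: "All analyses in this section will be performed using the Safety Population". SAP 3.1 defines that set as "all enrolled and randomized subjects who applied at least one treatment of the study drug", so membership needs one application but no follow-up visit and no later bottle weight.

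Among the compliance parameters, 5.2 lists "The number and percentage of subjects who received fewer than 60% of prescribed applications (and considered non-compliant with the treatment) at each visit", and the same over all follow-up visits. Compliance is C = (AW/EW) × 100. For AW, the plan says "The actual amount of drug applied in an interval (AW) will be the difference between the bottle weights at the relevant visits". The flag follows from the computed value: "if the value is less than 60%, then the subject will be considered non-compliant for that study treatment interval". Nothing is said about a subject for whom C cannot be computed.

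The denominator comes from the general rules. SAP 4.1.2 states that, absent another specification, "the denominator for calculating a percentage will be the total number of subjects in the analysis population for the subgroup being analyzed". Table 9.0 repeats it: "Denominator is the total number of subjects in a column group unless otherwise specified". Section 5.2 specifies no other denominator. By contrast, 6.1 (demographics) and 7.2 (tolerability) both replace the default with the number of subjects who supplied data.

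**The concern.** The numerator and denominator cover different subjects. Only subjects weighed at both ends of an interval can be flagged, but the whole arm is counted below the line. A Safety Set subject who left the study, missed the visit or came without the bottle lowers the percentage simply by being unmeasured. The error runs one way, towards less reported non-compliance, and it grows with the number of missing weights, which would usually be larger at later visits.

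The primary objective is safety against placebo, and this table describes how much product lay behind that comparison. A non-compliance figure that falls because bottles were not weighed is a poor guide to exposure. That 6.1 and 7.2 override the default, while 5.2 does not, suggests an oversight rather than a deliberate choice.

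**Working it through.** The plan gives no compliance percentage, so there is no figure to reproduce. The check is what the stated rule yields.

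**Inputs from the documents**
- 72 subjects, chosen so that at least 60 complete (SAP 2.2); up to 72 − 60 = 12 may not complete.
- 2:1 allocation (SAP 2.1), so 48 SAN021 and 24 placebo if all 72 are randomized.
- Denominator: all Safety Set subjects in the arm (SAP 4.1.2, Table 9.0, 5.2).
- Numerator: subjects with a computed C below 60% (SAP 5.2), reading AW as the product used between two weighings.

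**Assumptions, not in the documents**
- All 72 are in the Safety Set.
- The number without the needed weights (0, 6, 12 or 18 of 72).
- The non-compliance rate among weighed subjects (10%, 25% or 40%).

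**Formula.** Let k be the number flagged.
- Printed percentage = k / N_safety
- Percentage among weighed subjects = k / n_weighed
- Hence printed = (percentage among weighed) × (n_weighed / N_safety)

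**Dilution factor, both arms together**

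| Unweighed | n_weighed / N_safety | Factor | 25% is printed as |
|---|---|---|---|
| 0 | 72/72 | 1.000 | 25.0% |
| 6 | 66/72 | 0.917 | 22.9% |
| 12 | 60/72 | 0.833 | 20.8% |
| 18 | 54/72 | 0.750 | 18.8% |

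With 12 unweighed and 25% non-compliant, 15 of 60 are flagged: 15/60 = 25.0% among weighed subjects and 15/72 = 20.8% in print. At 10% and 40%, the printed figures are 6/72 = 8.3% and 24/72 = 33.3%. If all 12 unweighed subjects were in truth non-compliant, the 25% case would be (15 + 12)/72 = 37.5%. The printed value therefore lies at the bottom of the possible range.

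**By arm, with 25% among weighed subjects in both arms**
- Loss in proportion to arm size (8 SAN021, 4 placebo): 10/48 = 20.8% and 5/24 = 20.8%. Both are diluted, with no difference between arms.
- Uneven loss (4 SAN021, 8 placebo): 11/48 = 22.9% and 4/24 = 16.7%, a difference of 6.2 points with no true difference.
- All 12 in SAN021: 9/48 = 18.8% and 6/24 = 25.0%. All 12 in placebo: 12/48 = 25.0% and 3/24 = 12.5%.

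Because each AW also needs the preceding weight, one missed weighing can leave two consecutive intervals without a C.

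**The case against.** Much of what a reader needs is planned elsewhere. Visit attendance is tabulated by arm and visit. Quantitative parameters, including total product weight, carry their own n. Counts stand beside percentages, and dispensation and compliance are listed by subject. The table shells are a separate document and may carry a denominator note. The Protocol synopsis asks sites to try to bring interrupted patients back for a final visit, where the bottle is weighed, so leaving early does not always mean going unweighed. No test uses this percentage.

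All of that stands, and it limits the importance of the point. It does not correct the percentage. Attendance does not show how many bottles were brought, an n on a weight summary does not change the divisor of another row, and the SAP text as written leads to the full-arm denominator.

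Three stronger readings are tempting but are not supported.
- A reader might infer that the SAP classes unweighed subjects as compliant. It does not: it reports only the non-compliant, and the dilution is an arithmetic effect.
- A reader might infer that the Per Protocol set is compromised. SAP 3.3 excludes for "Noncompliance (i.e., less than 60% compliant with study treatment), as determined by the average product usage for the duration of participation", not for the by-visit percentages, and the overall C in 5.2 uses the most recent recorded weight, so one missed weighing does not remove it. A subject with no Day 42 observation is already excluded. What remains is a subject seen at Day 42 whose bottle was never weighed at any follow-up visit, and the documents do not settle whether even that subject lacks a C.
- A reader might infer a false difference between arms or a false improvement over time. The first needs missingness that differs by arm, and the 4-and-8 example means 33% of placebo weights missing against 8% of SAN021. The second depends on how true non-compliance moves over the visits. Neither can be known from the documents.

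**Conclusion.** The point holds. Followed as written, SAP 5.2 with 4.1.2 and Table 9.0 understates the by-visit percentage of non-compliant subjects, relative to those who could be assessed, by the factor n_weighed / N_safety. At the plan's allowance of 12 non-completers, if all are unweighed at Day 42, the factor is 0.833. With complete weights there is no distortion.

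The sizes rest on assumed rates and missing counts, and on shells that do not override the SAP. The consequence is limited to one row of a descriptive exposure table in a trial without inferential analyses. The figure over all follow-up visits is much less exposed, and no change to the Per Protocol definition follows. This is a minor correction, worth making because it changes a reported number.

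**What to change.** In SAP 5.2 and Table 14.2.1.2:
- State that the denominator of the by-visit non-compliance percentage is the number of subjects in the arm with a computable C for that interval, and print that n.
- Add a row by arm and visit, *compliance not evaluable (no bottle weight)*, with the Safety Set as its denominator.

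The second item keeps the Safety Set visible, so no information is lost and a reader can see whether missing weights differ between arms. The cost is a sentence or two in the SAP, a printed n and one table row. No new data are needed, and SAP 3.3 is left as it is.

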- Perform a full physical examination including height (cm) and weight (kg).
- Record pertinent medical history including tobacco, illegal substance and alcohol history and current use.
- Administer the Physician's Global Assessment (PGA) and the Psoriasis Area Severity Index (PASI).
- Calculate the plaque BSA of the area(s) to be treated.

Treatment Period

Visit 1 Baseline (Day 1 [± 2 Days])

Eligible subjects will have the following procedures completed at Visit 1 (Baseline). It is possible for the patient to be screened and complete the Visit 1 (Baseline) procedures on the same day.

- Review inclusion and exclusion criteria to ensure the patient qualifies for the study.
- If this visit is NOT combined with the screening visit:
 - Perform an abbreviated physical examination including weight (kg),
 - Update concomitant medications including all prescription drugs, non-prescription drugs and nutritional supplements
 - Review and update the patient's pertinent medical history.

- Complete the PGA (only treatment area(s) are to be evaluated), PASI and tolerability assessment (only treatment area(s) are to be evaluated) including calculating the BSA of the affected area (only treatment area(s) are to be evaluated).
- If patient is a female of childbearing potential, collect a urine sample and perform a β -human chorionic gonadotropin pregnancy test.
- Instruct the patient on proper washing of the target treatment area(s) (using only study-approved cleanser) and application of SAN021 study medication on the treatment areas during the treatment period.
- Photograph the treatment area(s).
- Replace the cap with the dropper cap and weigh full bottle of SAN021 study medication and record weight prior to on site first dose.
- With the dropper cap on, weigh bottle of SAN021 study medication post on site dose and dispense to subject.
- Instruct the subject to return in one week for the next study visit with the study drug

Visit 2 (Day 7 [± 2 Days]), Visit 3 (Day 14 [± 2 Days]), Visit 4 (Day 28 [± 2 Days])

All study visits have a ± 2 -day visit window.

- Query for adverse events.
- Update concomitant medications including all prescription drugs, nonprescription drugs, and nutritional supplements.
- Query for treatment regimen compliance.
- Weigh and record the weight of the study medication and re-dispense.

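### SAP 5.2 subtracts the bottle weights in the wrong order, so for a single bottle the compliance percentage is the exact negative of what is meant

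*SAP*

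**What the plan says.** SAP 5.2 introduces AW in words: "The actual amount of drug applied in an interval (AW) will be the difference between the bottle weights at the relevant visits". The formula printed below it is "AW = \text{weight of bottle at current visit} - \text{weight of bottle at previous visit". Compliance is C = (AW/EW) x 100, described as use relative to expected use. Expected weight is EW = X x W, where W is baseline BSA times 0.25 and X is the number of applications in the interval. The section says of C that "This value may be greater than 100" percent, and it treats an interval with C below 60% as non-compliant.

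For the whole treatment period the section adds: "Using these same calculations, compliance over all follow-up visits will be calculated using available data from the medication dispensation log". Use from a bottle is "the difference of the last medication weight reported and the weight of the bottle at dispensation", and "If multiple bottles are used, cumulative product weight will be calculated".

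In the protocol, the instruction for Visits 2 to 4 is "Weigh and record the weight of the study medication and re-dispense". At Visit 1 the site is to "weigh full bottle of SAN021 study medication and record weight prior to on site first dose", and then to weigh the bottle again after that dose when it is dispensed to the subject. Both Day 1 weights are therefore recorded.

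**The concern.** An amount applied cannot be negative, yet the printed subtraction gives a negative number whenever any product is used from one bottle. The 60% rule would then classify every such interval as non-compliant, however well the subject adhered.

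The direct casualty is the by-visit non-compliance count in Table 14.2.1.2. Listing 16.2.6.2 carries compliance in its title and may show the same values, but the shells are in a separate document, so this cannot be confirmed. SAP 3.3 makes product use below 60% over the duration of participation a major violation, so the overall version of C also helps decide who is in the Per Protocol set. That set supports the efficacy tables and is counted in the disposition table.

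**Working it through.** The SAP gives no numerical compliance value, so there is no printed figure to reproduce. The check is algebra plus an example.

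**Inputs**
- AW, EW, W, X, C and the 60% cut: SAP 5.2.
- Study Day = date - baseline date + 1: SAP 9.0. Nominal Days 7, 14, 28 and 42 are therefore 6, 13, 27 and 41 days after baseline.
- Visit window of ±2 days: SAP Table 2.1.
- Baseline BSA of 1% to 10%: protocol inclusion criterion 2.
- Same bottle weighed and returned: protocol, Visits 2 to 4.

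**Step 1. Application counts.** From baseline, X = 2n + 1 for n days; between follow-up visits, X = 2n.
- Day 1 to 7: 2 x 6 + 1 = 13
- Day 7 to 14: 2 x 7 = 14
- Day 14 to 28: 2 x 14 = 28
- Day 28 to 42: 2 x 14 = 28
- Day 1 to 42: 2 x 41 + 1 = 83, which equals 13 + 14 + 28 + 28

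X agrees with the section's own counting rule (two applications on Day 1, one on each visit day, two on other days), so X is not the source of the sign problem.

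**Step 2. Sign of C, single bottle.** Let P be the previous and R the current bottle weight, with R ≤ P.
- Printed: C = 100 x (R - P)/EW
- Intended (used over expected): C = 100 x (P - R)/EW

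EW is positive because X > 0 and W is at least 1 x 0.25 = 0.25. Hence printed C = -(intended C) for any BSA, interval or weight unit.

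**Step 3. Example with BSA = 5.** W = 5 x 0.25 = 1.25.

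| Interval | X | EW | Use as % of expected | Intended C | Printed C | Printed C below 60%? |
|---|---|---|---|---|---|---|
| Day 1 to 7 | 13 | 16.25 | 60 | 60% | -60% | yes |
| Day 1 to 7 | 13 | 16.25 | 100 | 100% | -100% | yes |
| Day 14 to 28 | 28 | 35 | 80 | 80% | -80% | yes |
| Day 28 to 42 | 28 | 35 | 120 | 120% | -120% | yes |

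The intended C is below 60% in none of these rows. Under the printed formula a single bottle can never give more than 0%, which contradicts the statement that C may exceed 100%.

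**Step 4. Day 1 weight against X.** X includes both Day 1 applications. The overall rule starts from the weight at dispensation, and the protocol dispenses the bottle with the weighing that follows the on-site dose. Read together, these point to the post-dose weight, so one counted application is missing from the measured use. Assume that the post-dose weight is used (for the Visit 2 interval as well as overall), that the on-site dose equals one expected application W, and that the subject is otherwise fully compliant. With the sign corrected, C = 100 x (X - 1)/X:
- Overall, nominal Day 42: 82/83 = 98.8%
- Visit 2, nominal Day 7 (6 days): 12/13 = 92.3%
- Visit 2, earliest in window (4 days, X = 9): 8/9 = 88.9%
- Visit 2, latest in window (8 days, X = 17): 16/17 = 94.1%

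**The case against.** The best defence is that this is a slip of notation. The prose around the formula allows only a positive AW: an amount applied, a ratio of used to expected, a value that can pass 100%. The verbal definition is an unsigned difference, and a programmer who saw nothing but negative compliance would notice. SAP 3.3 also reports that the threshold was lowered from 80% to 60% after medication use was examined before unmasking, which makes sense only if use was being read as positive. The trial has no inferential analyses, and the FAS is the primary efficacy set.

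All of this stands, and it limits the consequence. It does not make the formula right: this is an operative derivation rule, and nothing elsewhere in the SAP reverses the sign or calls for an absolute value.

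Two stronger readings are tempting and are not supported. A reader might infer that the Per Protocol set would be emptied. The overall rule is worded as an unsigned difference, so that follows only if the sign is imported through the reference to the same calculations. A reader might also infer large errors from bottle replacement, because the cumulative rule appears only in the overall paragraph. If a bottle is replaced at a visit and the next interval starts from the new bottle's weight, the reversed formula works. Trouble needs a change within an interval, or several bottles in use together. The supplied text schedules neither and gives no bottle weights, so no size can be put on it. Stating the rule per interval is a clarification only.

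**Conclusion.** The printed AW formula is wrong as written. For a single bottle, C is the exact negative of the intended compliance; this rests only on the bottle not gaining weight between visits. Followed literally, every single-bottle interval counts as non-compliant in Table 14.2.1.2. Overall compliance, and through it the Per Protocol set, is affected only if the sign is carried over. FAS efficacy and safety are unaffected. Severity is minor, and the documents do not show that any result was computed with the wrong sign.

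The Day 1 mismatch is smaller: about 1.2 points overall (1/83) and 5.9 to 11.1 points at Visit 2 (1/17 to 1/9), under the assumptions in step 4. It would be too strong to say that the SAP leaves the starting weight wholly open, since the overall rule names the weight at dispensation. The problem is that this weight, as the protocol takes it, does not match X.

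**What to change.** In SAP 5.2:
1. Print AW = weight at previous visit - weight at current visit.
2. State overall use for each bottle as weight at dispensation - last reported weight, summed over bottles.
3. Apply the same per-bottle sum to any interval in which more than one bottle is used, taking the previous-visit weight as the starting weight of a bottle carried into the interval.
4. Choose one consistent Day 1 pair and use it for both the by-visit and the overall measure. Either take the pre-dose Day 1 weight with X as printed, saying that this replaces the dispensation weight for the first bottle, or take the post-dose weight and reduce X by one for intervals that start at baseline (X = 2n). The second choice gives 82/82 overall and 12/12 at nominal Day 7 for the fully compliant subject in step 4.

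The cost is SAP wording and the matching derivation code. The protocol already records both Day 1 weights, so no new data are needed.
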